#### **Secondary Outcome Measures:**

- Barthel index and Modified Rankin Score: change from baseline (measured when receiving the device) at the end of the rehabilitation treatment (when returning the device)
- Time dedicated by the specialised personnel to each patient for training to learn the WeReha device before leaving the trial site (measured in minutes/patient)
- Number of calls per week for clinical and technical assistance specific for the WeReha device, registered on a paper or software spreadsheet by the sponsor

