- ii)     ii) how to position the sensor inside it,
- iii)     iii) how to move the object in order to reach the game’s target.

Once the sensor is worn or positioned inside an object, before starting the game, the patient is guided through a calibration phase to measure the sensors initial orientation in the space which acts as a reference position for all the movements recorded during the game. This process not only makes the measures more accurate but also nullifies any sensor wrongly positioned when worn (i.e. sensor overturning, rotations, inclinations respect to the body frontal plane).

In this pilot study investigators will recruit as many patients as possible as defined within the inclusion and exclusion criteria. There will be 75 devices available at the site from September 2018 to December 2019. Each patient will be provided with a WeReha device including the tablet and its charger, the inertial sensor and its charging station and cable, a kit of elastic straps together with a Velcro pocket and the 3 plastic objects. Every device can be used twice in order to assess as many patients as possible, providing a new set of straps and smart objects (that are to be considered single user only) and cleaning the other components by following specific and simple instructions provided by CoRehab.

Participants will be consented following a diagnosis of stroke and will keep the device for a maximum of 20 weeks following discharge from the hospital setting. This amount of time has been decided following review by clinicians and therapists during our earlier feasibility work. After that the tablet and the sensor will be collected, cleaned to ensure no cross contamination and meeting infection control guidelines within each Trust and made available for further use... The elastic straps with the pockets and the smart objects are the only personal and single use components, which will be disposed of after use... Secondary outcomes will only be assessed on “active patients”.

There will be a WeReha server available as a cloud solution, compliant with NCSC Cloud Security Principles, on which the web application will run and all the data will be collected whenever a patient’s device is connected to the internet. It is important to highlight that internet connection is not mandatory for the device to work properly as it will propose exercises to the patient as they were prepared initially after patient’s discharge. Then, whenever the device is

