connected either through Wi-Fi or cellular network, data will be uploaded to the server through a secure VPN or https protected connection, or at the very latest when the device is returned to the hospital. However, for the sake of the study, we will provide a prepaid internet card to all participants requiring it. Patients data will be always uploaded and maintained in an anonymised form and stored following stringent security and privacy principles.

Data relative to the primary outcome will be collected automatically on the device and uploaded to the server whenever possible. Clinical measurements (such as scales and scores) will be assessed only when starting the study and when returning the device.

WeReha includes a password protected administration area accessible only by the dedicated figure, through which it is possible to manage the reset of data in the local memory once the device is collected and then re-assigned to another patient. In addition, every tablet is provided with a software program installed for a quick and effective remote assistance by the technical staff of the sponsor directly on the patient's WeReha device (Bomgar SW, [www.bomgar.com](http://www.bomgar.com)). This is intended as a second level support to patients and will only be required if the dedicated figure cannot solve the issue on which the assistance was sought. WeReha requires an internet connection at patient home in order to allow Corehab's remote intervention.

Following admission to Belfast or South Eastern Trust stroke units, patients will be pre-screened against the inclusion and exclusion criteria. Those who appear to fulfill the criteria will be highlighted by nurses and therapists to the recruiting therapist. Patients will be provided with all the study details and patient information sheet (PIS) to review. A screening log will be used to track the number of patients that are approached to participate. If the patient is ineligible or refuses to participate, the reason will be recorded in the log, if they so choose to provide us with reasons for the same.

In some cases, patients who have been discharged from the stroke units to the community may be identified as appropriate for the study. In this case the relevant Trust PI will provide them with the PIS and access for clarification.

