#### Inclusion criteria:

- Ages Eligible for Study: Over the age of 18
- Sexes Eligible for Study: All
- First-time ischemic or haemorrhagic stroke, as documented by a CT or MRI
- Patients able to sit for at least ten minutes and to look after own affairs without assistance i.e. a Modified Rankin Scale (MRS)≤ 2
- Montreal Cognitive Assessment (MoCA) ≥12
- Ability and willingness to participate in the study
- Complete a signed consent form

Exclusion criteria:

- Significant medical conditions that affected function prior to the stroke and would limit normal stroke rehabilitation (e.g. musculoskeletal condition affecting arm function or cardiac condition limiting basic activities of daily living).
- Bilateral weakness of upper extremities
- Unavailability of a caregiver
- Participation in another clinical trial involving rehabilitation (recreational therapy, occupational therapy, physiotherapy) or an investigational drug.

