## Data Management and Statistical Analysis

As the primary outcomes of the study are designed to evaluate the impact and acceptance of a new rehabilitative technology for stroke patients, a statistical analysis on the primary outcomes will not be conducted. On the other hand, the study clearly aims to evaluate the number of patients, meeting the inclusion/exclusion criteria that are willing to use this technology and the time they will be using the devices at home. It has also to be noted that this study is part of a research project (Magic-PCP, [5]) where 3 companies will provide their solutions to 1 hospital in Italy and sites in NI, i.e. each company will run a similar trial with identical numbers on different sites. The request and the funding to provide 75 devices on each country and aim at performing a validation on maximum 2 patients per device is a clear requirement of the project. We have then defined the primary and secondary outcomes that we consider crucial for evaluating our proposed technology.

The primary outcome will be evaluated in an anonymised form and considered good if planned KPIs are met or exceeded. Secondary outcomes will be evaluated using an unpaired test to compare pre and post intervention measured values, whereas the Chi-square test will be used to detect the significance of outlier proportions, p values smaller than 0.05 will be considered statistically significant. All calculations will be performed using the Matlab software tool (The Mathworks Inc., Natick, MA, USA). We are also interested in evaluating possible correlations among results for the different groups of patients under examination (male and female <55 years old, 55-70, more than 70) to be better prepared for a future clinical investigation of our device.

All details related to the Data Management are provided in Annex A - Technical Data Management of the present document.

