Where Data is stored and how it is protected at rest	This information is stored locally to the patient device. It is also sent via an encrypted channel to the WeReha Clinical Application along with patient's answers to questionnaires (Patient_Safety_Quest) and stored along with the Patient_Clinical_Data records.
Who can access data	Refer to Patient_Clinical_Data

Data retention period	Refer to Patient_Clinical_Data
------------------------------	--------------------------------

ID	Anonym_Patient_Record
Description	For each patient, a record containing (5 years) age range, gender, the results of the daily exercise sessions performed by the patient, diagnosis and diagnostic data (e.g. Berger scale score, Rankin score) available at the beginning of the treatment period and evaluated at the end of it.
Purpose of data collection	To enable the evaluation of WeReha system performance/adaptation/behavior as well as the measurement of the research study primary and secondary outcomes.
How Data is collected	WeReha provides a tool to export anonymized patient records from the system.
Where Data is stored and how it is protected at rest	N/A
Who can access data	Anonym_Patient_Report are accessed by CoRehab for statistical data analysis and outcomes measurements.
Data retention period	N/A

ID	Patient_Informed_Consent
Description	Patient Informed consent (paper document)
Purpose of data collection	The signed informed consent is mandatory for participating in the WeReha - Magic clinical trial.

How Data is collected	A hard copy of the informed consent form is provided by the dedicated figure in person to those patients who manifested interest to participate to the WeReha - Magic clinical trial. Only informed consent signed by hand by the patient in person (or by his/her caregiver when applicable) will be accepted for participating.
Where Data is stored and how it is protected at rest	Patient_Informed_Consent will be kept in hospital repositories in rooms the access of which is permitted to authorized medical staff only and according to existing policies.
Who can access data	The dedicated figure (and possibly other authorized members of hospital staff involved in the clinical trial).
Data retention period	The retention period of the informed consent is determined by HSC policies.

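### Barthel and Rankin scores before and after treatment come from the same patients, but the plan compares them with an unpaired test

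*Combined protocol and SAP*

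**What the plan says.** Under Data Management and Statistical Analysis the protocol states: "Secondary outcomes will be evaluated using an unpaired test to compare pre and post intervention measured values". The same sentence adds a chi-square test for what it calls outlier proportions and closes with "p values smaller than 0.05 will be considered statistically significant". It does not say whether the unpaired test is a t-test or a rank test, or whether it is two-sided.

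Four other places show what data the test would receive:

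- Secondary Outcome Measures defines the endpoint as "Barthel index and Modified Rankin Score: change from baseline (measured when receiving the device) at the end of the rehabilitation treatment", that is, when the device is handed back.
- Study Design says: "Clinical measurements (such as scales and scores) will be assessed only when starting the study and when returning the device".
- Study Design also limits the analysis set: "Secondary outcomes will only be assessed on" active patients.
- Annex A describes an anonymised record for each patient, with diagnostic scores "available at the beginning of the treatment period and evaluated at the end of it". The sponsor uses this record for the statistical analysis.

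No section describes a control group, a paired analysis, or a reason for setting the pairing aside.

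**The concern.** An unpaired test assumes that the two sets of values come from independent groups. Here each post value belongs to a patient who also supplied a pre value. The test builds its standard error from the spread between patients at each time, although what matters for a change is the spread of the individual changes. If patients who start high tend to finish high, the individual changes vary much less than the raw scores and the unpaired standard error is too large.

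The error is conservative, but that does not make it harmless. Barthel and Rankin are the only clinical scores among the outcomes, and the plan applies a 0.05 threshold to them. An improvement, or a deterioration, could be reported as not significant only because the pairing was ignored. Of the listed secondary outcomes only these two have a pre value, so the sentence governs exactly them.

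**Working it through.** The plan gives no sample size, power, SD or correlation for these scores, so there is no figure of its own to reproduce.

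**Inputs.** From the documents: alpha 0.05, and 40 active patients (a minimum target under Primary Outcome Measures, not a powered sample size). Assumed: a two-sided test, equal SDs before and after, pre–post correlation ρ from 0.3 to 0.9, and true changes of 0.3 and 0.5 SD.

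**Standard errors** for n patients measured twice:

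- unpaired: SD × √(2/n)
- true SE of the mean change: SD × √(2(1−ρ)/n)
- ratio: 1/√(1−ρ), which is 1.20, 1.41, 1.83 and 3.16 at ρ = 0.3, 0.5, 0.7 and 0.9

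**Type I error** of the unpaired test: 2 × [1 − Φ(1.96/√(1−ρ))]. At ρ = 0.5 this is 2 × [1 − Φ(2.77)] = 0.0056.

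**Power, worked once** (ρ = 0.5, change 0.3 SD, n = 40). The unpaired SE is √(2/40) = 0.224, so the rejection limit is 1.96 × 0.224 = 0.438. The true SE is √(1/40) = 0.158.

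- unpaired: Φ((0.3 − 0.438)/0.158) = Φ(−0.87) ≈ 19%
- paired: Φ(0.3/0.158 − 1.96) = Φ(−0.06) ≈ 48%

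Simulated t-tests give 19% and 46%; the small gap is the t correction at n = 40.

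**Simulated t-tests, n = 40:**

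| ρ | Type I error, unpaired | Power at 0.3 SD, unpaired vs paired | Power at 0.5 SD, unpaired vs paired | Change detectable with 80% power (SD), unpaired vs paired |
|---|---|---|---|---|
| 0.3 | 2.0% | 23% vs 35% | 62% vs 74% | 0.60 vs 0.54 |
| 0.5 | 0.7% | 19% vs 46% | 64% vs 87% | 0.58 vs 0.45 |
| 0.7 | 0.06% | 14% vs 67% | 67% vs 98% | 0.55 vs 0.35 |

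At ρ = 0.9 the detectable change is 0.51 SD unpaired against 0.20 SD paired. The paired test holds its type I error at about 5%. In terms of a single result, a paired p of 0.01 would appear as about 0.03, 0.07 and 0.16 at ρ = 0.3, 0.5 and 0.7 (normal approximation).

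**Direction.** At ρ = 0 the two tests are about equal. At ρ = −0.2 the unpaired test would be anti-conservative (type I error 7.4%). Positive correlation is the reasonable expectation for one patient's disability score measured twice.

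**Rankin.** Entry requires "a Modified Rankin Scale (MRS)≤ 2", so baseline has only three levels and normal theory is a rough guide. Assume 15%, 35% and 50% of 40 patients at scores 0, 1 and 2, with one-grade changes only.

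- *Mostly improving:* 30% of those above 0 improve and 5% of all worsen. Expected numbers are 40 × 0.85 × 0.30 = 10.2 improved and 40 × 0.05 = 2 worsened, so about 12 changed. Power is about 8% for the rank-sum test against 69% for the signed-rank test with normal approximation, or about 59% with an exact test.
- *Mostly worsening:* 30% of all worsen and 5% of those above 0 improve. Expected numbers are 12 worsened and 40 × 0.85 × 0.05 = 1.7 improved, so about 14 changed. Power is about 10% against 86%, or about 79% exact.

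Repeat simulations moved the normal-approximation figures by about two points. A separate three-level score cut from a correlated normal variable (ρ = 0.7, shift 0.3 SD) gave 12% against 46%.

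**The case against.** The wording error itself is hard to dispute; the case on the other side concerns weight, size and cost.

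- **Sample size.** Forty is a minimum. With 75 devices in a country, each used by up to two patients, there could be 150. At ρ = 0.5 and n = 150, power for a 0.3 SD change is about 81% unpaired against 95% paired. In the improving Rankin scenario, rank-sum power rises to about 50% at n = 100 and 83% at n = 150. This stands: the power loss shrinks as numbers grow. The distorted type I error does not depend on n in this way.
- **Scenarios.** The Rankin distribution and rates of change have no source in the documents, and the normal-approximation powers flatter the signed-rank test. Barthel may bunch near its maximum in patients this independent, which the normal model ignores. These points stand as limits on the size, not on the direction under positive correlation.
- **Consequence.** This is a pilot judged on usage targets, and the error makes false claims of benefit rarer. A paired test would not attribute change to the device without a control group. Nor would it serve the stated aim, under Study goals and objectives, of comparison with standard values, for which no test is given. All true, and the reason this is not graded higher. None of it makes the named test suitable.
- **Data access.** Annex A says in its clinical-data entry that the sponsor's staff receive only aggregated clinical data, from which no paired test could be run. But the anonymised-record entry gives the sponsor individual start and end scores for outcome measurement, so pairing is available. Its examples name Rankin but not Barthel, so the Barthel field needs confirming.

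**Conclusion.** The plan is wrong as written: it applies a test for independent groups to two measurements on the same patients. This follows from the text alone and needs no assumption. Under positive within-patient correlation the result is inflated p-values and lost power for both improvement and worsening.

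The size is conditional. With about 40 active patients the loss is large for small changes or high correlation, and modest for larger changes at low correlation. It becomes smaller as numbers approach the device ceiling. These figures rest on assumed correlations, changes and Rankin distributions and should be read as a range. The effect is confined to the two secondary clinical scores. It should be corrected before analysis.

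**What to change.** Replace the unpaired-test clause under Data Management and Statistical Analysis with wording such as:

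> Barthel index and Modified Rankin Score at device return will be compared with baseline within the same active patients, using the Wilcoxon signed-rank test for Rankin and the signed-rank or paired t-test for Barthel (two-sided 0.05). The change will be reported with its 95% confidence interval and, for Rankin, the numbers improved, unchanged and worsened.

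Choose between the two Barthel tests before the data are seen; signed-rank is the safer choice if scores may cluster near the top of the scale. With so few Rankin levels and many unchanged patients, use the exact form of the signed-rank test. State how many active patients lack a return score.

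The cost is one sentence of analysis text. No extra patients, visits or measurements are needed. While editing, confirm that the anonymised record in Annex A carries Barthel as well as Rankin at both times, and align the aggregated-data statement with that record.

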## Anticipated Results of the Study

As stated, this trial is part of the Magic-PCP project [5], and the results of the study aim to demonstrate the impact of the usage of technology for stroke patients and community on a large scale. The project anticipates that devices will be accepted by patients and integrated in their home treatment routine, that they will use it regularly and with the expectation that it improves motivation and as a consequence their quality of life and motor functions.

Results will be collated by the buyers group also with other ongoing studies within the umbrella of the Magic PCP project and compared eventually with existing studies that we referred to.

## Ethics

The trial sponsor is committed to make use of the principle of “GOOD FAITH”. The user-centered approach that guided the WeReha system realisation is essential not only to assure its functioning according to the target group’s needs and requirements, but it is also aimed at achieving the user’s ethical acceptance of the system.

The trial sponsor confirms that all results and activities carried out in this research study will not raise security/safety issues nor EU-classified information as background and that they will comply with national and international regulations on dual-use goods or dangerous materials and substances.

Furthermore, the trial sponsor declares that:

- Every individual that participates as research subjects will be handled as individuals worthy of honour and respect.
- The research subjects will be free to choose about participating or withdrawing when they feel it is necessary and the informed consent to participant in the clinical trial and any product demonstration session must given freely. Both the Patient Information Sheet and the template for the informed consent are attached to this document.
- Reasonable steps will be taken to ensure the integrity of data, which means that data will be reliable for its intended use, accurate and complete.
- All research participants will be treated as equal participants contributing valuable information. In addition, the WeReha system has been designed to function without any legal, civil, economic, gender and social rights discrimination

### Data protection & research participant’s confidentiality

The trial sponsor declares that the principles of the European Regulation concerning the processing of personal data by the Community institutions and bodies as well as the Regulation on Privacy and Electronic Communications and the General Data Protection Regulation (GDPR) (Regulation (EU) 2016/679 will be followed in the whole research study. This commitment

implies that only the necessary amount of personal information will be collected for the purpose of this Research Study, that retention and disposal periods will be clearly defined and enforced, that personal information gathered for a specific purpose will not be used for purposes other than directed without the consent of the individual and that in the default setting of the system, the participant is already protected against privacy risks.

[Annex A - Technical Data Management Plan](#) provides the following information about all personal and health data involved in the research study: nature of data, purpose of data collection, tools and procedure for data collection, where data is stored and how it is protected at rest, who can access data, data retention period. The WeReha system implements proper security techniques that are acknowledged to be proactive measures to address personal and health data confidentiality. They include: authentication, authorization, data encryption in transit and at rest, pseudonymization for data processed within the system and anonymization of data that is exported for the validation by the solution technology provider to assess the system performance, adoption, and behaviour.

## **Budget and support for the Project**

This trial will be supported by the MAGIC-PCP [5] EU funded project in which CoRehab result currently as one of the 4 company that has entered phase 2 of the project. Three companies out of four will have access to phase 3, and in this case only the proposed study will be run.

## ANNEX A - DATA MANAGEMENT PLAN

This section provides details about how personal and health data involved in the research study are managed in the research study.

